5.2 Exclusion Criteria

Pregnancy
History of lung transplant,
Severe anemia (hemoglobin concentration $<$ 7 g/dL),
Liver disease (AST/ALT $>$ 3x ULN), kidney disease (GFR \leq 40 mL/min), or
granulomatous conditions
Patients taking steroids, cholesterol-lowering drug (cholestyramine), weight-loss
drugs (Orlistat) , statins, anti-tuberculosis drugs (rifampin and isoniazid),
phenobarbital, phenytoin, carbamazepine, immunosuppressant (cyclosporine,
tacrolimus) (33, 34)

5.3 Withdrawal Criteria

Subject can be discontinued from the study for any of the following reasons:
Subject's personal reasons
Other significant study related adverse events

6.0 STRATIFICATION/DESCRIPTIVE FACTORS/RANDOMIZATION SCHEME

6.1 Stratification factors: Not applicable

6.2 Descriptive factors. Not applicable

7.0 STUDY AGENT ADMINISTRATION OR INTERVENTION AND TOXICITY MANAGEMENT PLAN

7.1 Patients will be given a single dose, oral capsule of vitamin D3 based on measured 25-(OH) vitamin D level (25).

7.2 Drug studies:

AGENT	DOSE	ROUTE	DAYS	ReRx	NOTES
Cholecalciferol	600,000 IU	PO	1	Once	25-(OH) vitamin D \leq 25 nmol/L (\leq 10 ng/mL)
Cholecalciferol	500,000 IU	PO	1	Once	25-(OH) vitamin D 25-50 nmol/L (10-20 ng/mL)
Cholecalciferol	300,000 IU	PO	1	Once	25-(OH) vitamin D 50-75 nmol/L (20-30 ng/mL)

7.3 Criteria for removal from treatment

7.31 A patient may always be removed from treatment whenever he/she wishes.

7.4 Ancillary treatments.

Patients will not be allowed to take supplements containing vitamin D3 during the trial.

8.0 ASSESSMENT OF EFFICACY AND SAFETY

8.1 Side effects/Toxicities to be monitored.

8.11 Possible side effects of vitamin D include: hypercalcemia, nausea, appetite, thirst, frequent urination, constipation, vomiting, abdominal pain, muscle weakness, muscle and joint pain, confusion, lethargy and fatigue (14, 35, 36). To ensure safety of high dose vitamin D in CF patients, we will be assessing the patients' calcium, magnesium, phosphate, albumin and alkaline phosphatases levels, at screening and day 7.

8.12 Long-term toxicities to be monitored after completion of therapy. List side effects/toxicities and define levels.
Long-term vitamin D toxicities have not been determined. Single high intramuscular dose (600,000 IU) of vitamin D3 was shown to be safe in patients with osteoporosis (37), and accidental mega-dose of 2,000,000 IU was well

tolerated, with slightly elevated calcium levels in the first two weeks, in two nursing home patients (38), suggesting that high bolus dose of cholecalciferol is safe.

8.2 Dosage change based on toxicity. Not applicable.

8.3 Adverse Event Reporting: Procedures for reporting unexpected and fatal toxicity should be explained.

8.31 Any significant adverse events that occurs during the course of the study will be documented and reported. The types of event to be reported include Type of event to be reported and timing of reports.

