review of pediatric CF patients, majority of patients (79%) rapidly and safely achieved and sustained optimal 25OHD levels over a 12 month period with a single high-dose oral vitamin D3 (300,000 IU – 600,000 IU), also known as stoss therapy (25). However, approximately 20% of patients still could not achieve levels above 30 ng/mL. Wide inter-individual variability in response to vitamin D treatment has been previously reported in non-CF population, suggesting that fixed-dose approach to replacement therapy may not be effective in improving 25(OH)D status in CF (30). Poor oral bioavailability of ergocalciferol has been demonstrated in CF patients (31), which suggests that CF patients may potentially exhibit low absorption of cholecalciferol. Therefore, based on the degree of malabsorption of vitamin D and basal vitamin D status, supplementation should be tailored to individuals. In order to optimize the treatment of deficiency in CF, kinetic disposition of vitamin D must be well understood. However, there are very few data currently available describing the kinetics of both vitamin D and 25-hydroxyvitamin D, and to the investigator's knowledge, no studies have yet characterized the pharmacokinetic disposition of vitamin D in cystic fibrosis. Addressing this issue is crucial in effectively and safely correcting vitamin D deficiency in CF.

Our study hypothesis is that CF patients with vitamin D deficiency exhibit altered pharmacokinetics of vitamin D and 25(OH)D when compared to non-CF subjects with vitamin D insufficiency or deficiency.

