3.0 STUDY DESIGN

This is a pilot study to determine the pharmacokinetics-pharmacodynamics of vitamin D3 in CF patients. Clinically stable CF patients with a history of pancreatic insufficiency (n=6) and matching non-CF subjects (n=6) will be recruited in this study. The presence of pancreatic insufficiency will be based on a known CF genotype associated with pancreatic insufficiency. All subjects will be pre-screened for 25(OH)D status to include those with 25(OH)D levels below 30 ng/mL. The subjects will receive a single oral dose of vitamin D3, known as stoss therapy. The dose of stoss therapy will be based on patient's baseline serum 25-hydroxyvitamin D3 level. For CF patients, the dose will be administered with food and pancreatic enzyme supplement to maintain nutritional status. This dose was chosen because previous studies in pediatric CF patients demonstrated that a large single dose of up to 600,000 IU vitamin D3 raised and maintained sufficient 25(OH)D concentrations over 12 weeks without any signs of adverse events (25, 26).

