5.0 SELECTION AND WITHDRAWAL OF SUBJECTS

5.1 Inclusion Criteria (CF) :

Diagnosis of CF based on positive sweat chloride or known CF mutation
Patients with pancreatic insufficiency
Age \geq 18 years
Serum 25(OH)D concentrations below 30 ng/mL (75 nmol/L)

Inclusion Criteria (non-CF) :

Age \geq 18 years
Serum 25(OH)D concentrations below 30 ng/mL (75 nmol/L)

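### Section 5.2 sets no exclusion for raised screening calcium, so no written rule keeps such a subject from the single 300,000–600,000 IU dose

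*Combined protocol and SAP*

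**What the plan says.** Section 8.11 names hypercalcemia first among the possible side effects. To safeguard CF patients given the high dose, it says that "we will be assessing the patients' calcium, magnesium, phosphate, albumin and alkaline phosphatases levels, at screening and day 7". The Appendix I calendar places the safety laboratory panel at the same two visits and does not restrict it to the CF group.

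Section 3.0 describes the population: "Clinically stable CF patients with a history of pancreatic insufficiency (n=6) and matching non-CF subjects (n=6) will be recruited in this study". Under section 5.1, both groups must be at least 18 years old with 25(OH)D below 30 ng/mL. The CF group must also have a CF diagnosis and pancreatic insufficiency.

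Section 5.2 excludes pregnancy, lung transplant, hemoglobin below 7 g/dL, AST/ALT above three times the upper limit, GFR of 40 mL/min or less, "granulomatous conditions", and a list of interacting drugs. Serum calcium is not mentioned.

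Sections 7.1 and 7.2 set the single oral dose from the measured 25(OH)D: 600,000 IU at or below 10 ng/mL, 500,000 IU at 10–20 ng/mL and 300,000 IU at 20–30 ng/mL.

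**The concern.** The protocol measures calcium before dosing for a stated safety purpose and then attaches no consequence to the result. The omission stands out because section 5.2 already uses written cut-offs for other laboratory values, while the analyte most directly tied to the first-listed toxicity has none.

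What is at stake is subject safety; no analysis depends on this point. In a repeated-dose study a high calcium could lead to a smaller next dose or a stop. Here the whole amount is given on Day 0, and section 8.2 marks dose change for toxicity as not applicable. A decision to protect a subject who starts with raised calcium has to be made before the dose, and the plan contains no rule for making it.

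**Working it through.** The plan gives no figure to reproduce. The check is whether any section contains a rule that acts on the screening calcium.

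| Section | What it controls | Does it act on screening calcium? |
|---|---|---|
| 3.0 | CF patients clinically stable; non-CF subjects matched | No |
| 5.1 | Age and 25(OH)D; CF diagnosis and pancreatic insufficiency for the CF group | No |
| 5.2 | Numeric laboratory limits for hemoglobin, AST/ALT and GFR; named conditions and drugs | No |
| 5.3 | Withdrawal for personal reasons or study-related adverse events | No; a screening abnormality precedes the study agent |
| 7.1–7.2 | Dose by 25(OH)D | No |
| 7.31 | Removal at the patient's wish | No |
| 8.11 | Calcium and albumin measured at screening and Day 7 | Measured, but no action level |
| 8.2 | Dose change for toxicity | Not applicable |
| 8.4 | Data monitoring committee | Not applicable |
| Appendix I | Safety panel at screening and Day 7 | Scheduled, but no action level |

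The counts that matter are these:

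- Numeric laboratory limits in 5.2: 3 (hemoglobin, AST/ALT, GFR), of which 0 concern calcium.
- Dose tiers in 7.2 that take calcium into account: 0 of 3. Setting the amount by 25(OH)D is the intended scheme and is not itself a fault. It does mean that the dosing rule supplies no second check.
- Scheduled calcium measurements: 2 (screening and Day 7), of which 1 comes before the dose.
- Subjects: 6 + 6 = 12.

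Next, the evidence the protocol cites in support of the dose:

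- Section 1.0 describes a retrospective review of pediatric CF patients given 300,000–600,000 IU, in which the "majority of patients (79%) rapidly and safely achieved and sustained optimal 25OHD levels over a 12 month period".
- Section 1.0 also reports that 250,000 IU in adults with CF did not cause hypercalcemia, and that high single doses in non-CF populations did not significantly alter calcium.
- Section 8.12 cites 600,000 IU given intramuscularly as safe in osteoporosis. It also cites an accidental 2,000,000 IU in two nursing-home patients as well tolerated, with slightly raised calcium over the first two weeks.

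None of these is described as covering people whose calcium was raised before the dose. The summaries are short and say nothing on that point, so they support neither safety nor harm in that subgroup.

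Finally, the likely burden of a cut-off at the upper limit of normal. Assume that the reference range holds the central 95% of healthy people, so that 2.5% lie above it, and that subjects are independent. The chance that at least one of 12 healthy subjects is flagged on a first test is 1 − 0.975^12 = 0.26. If exclusion also requires a raised repeat, and the repeat were independent of the first test, the per-subject probability would be 0.025 × 0.025 = 0.000625. The chance of losing at least one of 12 would then be 1 − (1 − 0.000625)^12 = 0.0075. Repeat values in one person are correlated, so the true figure lies between 0.0075 and 0.26.

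**The case against.** The strongest reply is that the gap is narrow in practice and its consequence is not shown. Every subject must have 25(OH)D below 30 ng/mL, which makes vitamin D excess an unlikely cause of a raised baseline calcium. Granulomatous conditions and low GFR are excluded, and the CF patients must be clinically stable. The AST/ALT and GFR limits mean that the screening chemistry is probably read before dosing. Section 16.0 commits the study to Good Clinical Practice, and an investigator who sees a high calcium may well withhold the dose. The cited studies are reassuring, and the documents give neither the frequency of raised screening calcium nor the added risk from the dose in such a subject.

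Most of this stands as a limit on the weight of the point. It does not supply the missing rule. The low 25(OH)D requirement leaves other causes of raised calcium open. The disease exclusions do not act on the measured value, so a subject with raised calcium and none of those conditions stays eligible. Clinical stability is required of the CF group only. Judgement fixes no threshold, calls for no albumin adjustment and does not require a resolved result before Day 0.

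**Conclusion.** The concern holds. Neither section 5.2 nor any other part of the protocol contains a written rule that stops a subject with raised screening calcium from receiving 300,000–600,000 IU.

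The size of the risk cannot be estimated from the documents. In a 12-subject pilot few, possibly none, would be affected. The recommendation therefore rests on clinical prudence, not on a demonstrated harm: the dose cannot be taken back, only one of the two calcium values comes early enough to prevent it, and the correction is nearly free. It should be made, but it does not call the design into question. The conclusion assumes that the exclusion list is complete as published; it shows no sign of redaction.

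**What to change.** Add to section 5.2, for both CF and non-CF subjects: *Albumin-adjusted serum calcium above the laboratory upper limit of normal at screening; one repeat is allowed, and the subject is excluded if the repeat is also raised.* Use the local laboratory's adjustment formula, and require the result to be resolved before Day 0 dosing. Stating that the repeat decides keeps a single chance high value from excluding a healthy volunteer.

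As a minor clarification, reword section 8.11 so that it covers both groups, as the Appendix I calendar already does.

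The change uses calcium and albumin results already collected at screening. The cost is an occasional repeat draw and an occasional screen failure, which matters slightly more when only six subjects per group are sought. Dose tiers, sampling times, endpoints and analysis are unchanged.

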Cystic fibrosis (CF) is a lethal autosomal recessive disorder characterized by chronic airway infections, inflammation and obstruction, leading to progressive loss of lung function and ultimately respiratory failure. Vitamin D deficiency is highly prevalent in CF patients, affecting approximately 90% of patients with CF (17, 18). Malabsorption of fat-soluble vitamins, which is a result of exocrine pancreatic enzyme insufficiency, likely play a role in vitamin D deficiency (19). Over 85% of CF patients are affected by pancreatic insufficiency, which causes intestinal malabsorption of nutrients, such as vitamin D (20). In addition to malabsorption, other factors may also contribute to suboptimal vitamin D status, including reduced exposure to sunlight, reduced levels of vitamin D binding proteins and poor adherence to daily dosing (20-22). Inadequate vitamin D level is of particular concern for patients with CF as vitamin D deficiency has been associated with increased risk of respiratory infection and worsened pulmonary function (21).

Study Rationale

Despite the extensive literatures on adverse clinical outcomes associated with vitamin D deficiency and beneficial effects of vitamin D supplementation in the treatment of various inflammatory and infectious diseases, there are currently no proven treatment strategy that effectively achieves and maintains optimal serum vitamin D status in CF patients (23). For the treatment of vitamin D deficiency in CF, CF Foundation currently recommends 2,000 IU daily (24). However, because achieving adequate serum 25(OH)D levels is a challenge in CF, higher doses of vitamin D may be necessary to reach and maintain vitamin D sufficiency (25, 26). A pilot study of vitamin D supplementation in adults with CF experiencing pulmonary exacerbation revealed that high dose of vitamin D (250,000 IU) raised 25(OH)D levels while it did not cause hypercalcemia or significant changes in PTH concentrations (26), which indicates that this mega-dose of vitamin D3 is safe in CF patients. In addition, several studies in non-CF population have demonstrated that high single doses of vitamin D3 did not significantly alter the PTH or calcium levels (27-29). In a retrospective chart

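### Calcium is checked after the dose only on day 7; repeating the safety panel at the existing day 28 visit would be a cheap precaution against a missed late or persisting rise

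*Combined protocol and SAP*

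**What the plan says.** Section 8.11 names hypercalcemia first among the possible side effects of vitamin D and plans to measure "calcium, magnesium, phosphate, albumin and alkaline phosphatases levels, at screening and day 7". The safety-lab row of Appendix I marks the same two visits; its footnote describes the content only as a comprehensive metabolic panel. Section 8.11 introduces the tests with the words "To ensure safety of high dose vitamin D in CF patients", whereas the Appendix I row is not limited to one group. Section 3.0 adds that "matching non-CF subjects (n=6) will be recruited in this study", and the dose table in section 7.2 applies no group distinction.

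Section 11.0 and Appendix I schedule blood draws on days 28, 56 and 70 for vitamin D3, its metabolites and inflammatory markers. Those samples are iced and then frozen until assay. Vital signs and adverse events are recorded at the same visits. Section 8.2 reads "Dosage change based on toxicity. Not applicable", as fits a single dose.

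On prior experience, section 1.0 reports that in adults with CF a "high dose of vitamin D (250,000 IU) raised 25(OH)D levels while it did not cause hypercalcemia", and that in non-CF studies "high single doses of vitamin D3 did not significantly alter the PTH or calcium levels". Section 8.12 states "Single high intramuscular dose (600,000 IU) of vitamin D3 was shown to be safe in patients with osteoporosis" and describes an accidental 2,000,000 IU dose as tolerated, "with slightly elevated calcium levels in the first two weeks, in two nursing home patients". Sections 1.0 and 3.0 also describe single oral doses of up to 600,000 IU in pediatric CF as safe.

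**The concern.** The dose is chosen for its long action, and follow-up runs to day 70, but the laboratory check for the first-listed side effect stops at day 7. A rise present on day 7 would be seen. A later rise with symptoms could come to light at the adverse-event checks. The remaining case is a subject whose calcium is normal on day 7 and rises afterwards without symptoms. Nothing in the plan would show this in time to act, because the later samples are frozen and are not assigned a calcium test.

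What is at stake is the care of an individual subject. A later value could not alter a dose already given, but it would let the investigator repeat the test and follow that person. Safety is neither an objective nor an outcome measure, and the pharmacokinetic comparison is unaffected.

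**Working it through.** The plan gives no figure to reproduce here. The check compares the schedule with the cited evidence.

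**Schedule (sections 3.0, 8.11 and 11.0, Appendix I)**

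- Subjects: 6 CF + 6 non-CF = 12.
- Post-dose calcium values now: 12 × 1 = 12. With day 28 added: 12 × 2 = 24, so 12 extra panels.
- Follow-up after the last calcium check now: 70 − 7 = 63 days; 63/70 = 90%.
- With day 28 added: 70 − 28 = 42 days; 42/70 = 60%.
- Scheduled draws between day 7 and day 28: none.

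**Cited evidence against the trial doses (sections 1.0, 3.0, 7.2 and 8.12)**

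| Evidence in the protocol | Relation to the trial dose | What it says about calcium after day 7 |
|---|---|---|
| Pediatric CF, single oral 300,000–600,000 IU | Same range and route | Described as safe, with levels sustained over 12 months (section 1.0), and without adverse events over 12 weeks (section 3.0); no calcium schedule given |
| Adult CF, 250,000 IU | Trial doses are 300,000/250,000 = 1.2 to 600,000/250,000 = 2.4 times higher | No hypercalcemia; timing of the tests not given |
| Non-CF studies, high single doses | Doses not stated | No significant change in calcium or PTH; timing not given |
| Osteoporosis, 600,000 IU intramuscular | Top trial dose, different route | Described as safe; no calcium result given |
| Accidental 2,000,000 IU, two patients | 2,000,000/600,000 = 3.3 to 2,000,000/300,000 = 6.7 times the trial doses | Slight rise in the first two weeks |

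The last row is the only evidence on when calcium rises. Day 7 lies inside that window and day 28 after it. A day 28 value can therefore show a rise that starts late, or one that starts after day 7 and persists. A rise that comes and goes between days 7 and 28 would still be missed.

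**Rate.** The documents give no frequency for a late rise, so the number of cases the present schedule would miss cannot be calculated, and I offer no figure.

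**The case against.** The strongest reply is that the schedule is a deliberate and defensible choice. Text and calendar agree. The closest evidence covers the same doses, by the same route, in the same disease, and reports no harm over a period well beyond day 7. The only timing information puts the rise early, where day 7 already looks, so the added test falls where the documents show no signal. The protocol also scales the dose to baseline 25(OH)D, excludes subjects with GFR at or below 40 mL/min or granulomatous conditions, bars vitamin D3 supplements, and checks for adverse events at every later visit.

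Most of this stands, and it is why the point is a suggestion only. It does not remove the point. The same-dose data are pediatric, and the protocol does not say whether or when calcium was measured in them. The adult CF data are at a lower dose. Symptom checks cannot find a silent rise. Section 8.12 itself concedes that long-term toxicity is not established.

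A reader might also infer that non-CF subjects get no safety labs, because section 8.11 speaks of CF patients. The documents do not support that: the Appendix I row has no group limit and can be read as covering everyone. The wording only needs to be made explicit.

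**Conclusion.** The point holds as a low-cost precaution, to be considered. Each subject has one post-dose calcium value, on day 7, and the remaining 63 of 70 days have none. A symptom-free rise that begins after day 7 would not be detected under the plan.

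Two stronger readings are tempting and should be resisted. One is that the trial exposes subjects to a known late hypercalcemia risk. No late rise is documented anywhere in the protocol, and the cited experience is largely reassuring. The other is that a day 28 panel closes the gap. It shortens the unchecked tail to 42 days but leaves days 8 to 14, the later half of the only described rise window, without a measurement.

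The conclusion assumes that no calcium result is obtained after day 7 outside the written schedule, and that a day 28 panel is a small addition. The documents give no costs, so the latter is a judgment.

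**What to change.** In section 8.11 and the Appendix I safety-lab row:

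1. Add the section 8.11 panel (calcium, albumin, phosphate, magnesium, alkaline phosphatase) at the existing day 28 visit, and name these analytes in the calendar footnote.
2. State that the panel applies to all 12 subjects, CF and non-CF.
3. Run it promptly on a fresh sample and not on the frozen pharmacokinetic aliquots.
4. Set an action rule for both the day 7 and the day 28 value: albumin-adjusted calcium above the local laboratory's upper limit is repeated and the subject followed clinically.
5. Limit any statement about calcium safety to the days on which calcium was measured.

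Cost: about 12 routine panels, possibly one extra tube per subject with prompt handling, and occasional repeat tests. No scheduled visit is added, and the pharmacokinetic analysis does not change.

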12.0 DATA COLLECTION AND MONITORING

Data will be collected on case report forms, which will be retained for the duration of the study. Data will include subject demographics, clinical characteristics, laboratory data, and results of pharmacokinetic analyses. Data will be coded and stored on a password protected electronic database.

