Appendix I: Study Calendar

Appendix I

	Screening	Day 0	Day 1	Day 7	Day 28	Day 56	Day 70
Informed Consent	X						
Medical History	X						
Medication History	X						
Height, weight	X						
Vital signs ^A	X	X	X	X	X	X	X
Safety labs ^B	X			X			
Pre-screening of 25OHD status	X						
PO drug administration		X					
Blood Pharmacokinetics (PK) ^C		X	X	X	X	X	X
Blood inflammatory biomarkers		X	X	X	X	X	X
Adverse Events		X	X	X	X	X	X

A. Vital signs to include blood pressure, heart rate, temperature, respiratory rate.

B. Safety labs to include comprehensive metabolic panel

C. All subjects will have a pre dose blood PK levels, 2, 4, 6, 8 hours and 1, 7, 28, 56, 70 days post dose of cholecalciferol. A 5mL serum separator tube will be used to collect the blood sample.

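### Section 8.31 commits the trial to documenting only adverse events judged *significant*, a term left undefined, so mild symptoms found at the scheduled visits need not be recorded

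*Combined protocol and SAP*

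**What the plan says.** - **What is to be watched for.** Section 8.11 names the possible side effects, beginning "hypercalcemia, nausea, appetite, thirst, frequent urination, constipation, vomiting, abdominal pain, muscle weakness" and ending with lethargy and fatigue. It also sets the safety chemistry: "calcium, magnesium, phosphate, albumin and alkaline phosphatases levels, at screening and day 7".
- **When it is assessed.** Section 9.0 refers to Appendix I. The calendar there has a row headed "Adverse Events", marked on days 0, 1, 7, 28, 56 and 70 with no severity limit. Safety labs are marked at screening and day 7. Vital signs are marked at every visit.
- **What is written down.** Section 8.31: "Any significant adverse events that occurs during the course of the study will be documented and reported". The sentence after it is still a template: "The types of event to be reported include Type of event to be reported and timing of reports". Section 8.32 names the IRB as the place for reports.
- **What the case report forms hold.** Section 12.0: "Data will include subject demographics, clinical characteristics, laboratory data, and results of pharmacokinetic analyses".
- **What is summarised.** Section 13.1 gives descriptive statistics for demographics, clinical characteristics and pharmacokinetic parameters. No part of section 13 mentions adverse events.

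**The concern.** Documenting an event and reporting it to the IRB are different acts and normally have different thresholds. Section 8.31 joins them under one adjective, defines that adjective nowhere, and gives no grading scale. Many of the symptoms in 8.11 are ones that an investigator could reasonably judge not significant when they are mild, although 8.11 presents them as things to monitor.

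Two things are at stake. The first is patient safety after a single dose of 300,000 to 600,000 IU: an early symptom that is not written down cannot be followed from one visit to the next. The second is even capture. The comparison is CF against non-CF, disease group is known to the assessor, and complaints such as abdominal pain or fatigue are easier to put down to the underlying disease in a CF subject. An undefined threshold leaves room for the same complaint to be recorded in one group and passed over in the other.

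**Working it through.** The plan states no figure on this point, so the check is a comparison of passages with a little arithmetic on the calendar.

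**1. Does any passage other than 8.31 say which events are recorded?**

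| Place | Question it answers | Does it say mild events are recorded? |
|---|---|---|
| 8.11 | What might occur | No |
| Appendix I, adverse event row | When to assess | No; there is no severity limit, but also no recording rule |
| 8.31 | What is documented and reported | Only *significant* events are promised |
| 12.0 | What data are collected | Adverse events not named |
| 13 | What is summarised | Adverse events not mentioned |

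Section 8.31 is the only place with a commitment about documenting, and that commitment stops at *significant*.

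**2. Walk one case through the text.** A subject reports new thirst and constipation on day 28. Appendix I requires the assessment. Section 8.31 requires documentation if someone judges the complaint *significant*, with no criterion to apply. Sections 12.0 and 13 name no field or table for it. A site that writes nothing has broken no stated rule; a site that writes it down has broken none either. The text does not settle which happens.

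**3. How much of follow-up depends on this?** Last safety chemistry: day 7 (8.11 and Appendix I agree). Last visit: day 70 (11.0 and Appendix I).

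- Time without scheduled safety chemistry: 70 − 7 = 63 days; 63 / 70 = 90% of follow-up.
- Adverse event assessments in that period: days 28, 56 and 70, so 3 per subject. With 6 + 6 = 12 subjects (section 3.0) and full attendance, 3 × 12 = 36 assessments.

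**4. Is anything else observed in that period?** Yes. Vital signs are taken on the same days: "Vital signs to include blood pressure, heart rate, temperature, respiratory rate". They are not specific to hypercalcemia. Blood is also drawn for vitamin D3 and 25(OH)D3, but section 11.0 has the samples stored frozen until analysis, and those assays do not measure calcium. Symptoms are therefore the only scheduled signal aimed specifically at hypercalcemia after day 7.

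**5. Does the protocol give reason to look past day 7?** Section 8.12 cites an accidental overdose of 2,000,000 IU with slightly raised calcium over the first two weeks. That dose is well above those used here, so it is only indicative, but the period extends beyond the last chemistry test.

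**The case against.** The strongest reply is that 8.31 is a reporting rule. It stands under a heading about reporting unexpected and fatal toxicity and is followed by the address for reports. It promises to document significant events; it does not say that others are left out. Routine capture would then come from Appendix I, whose adverse event row has no severity limit. Section 12.0 introduces its list with a verb that need not be exhaustive, leaves clinical characteristics undefined, and also omits vital signs and medication history, which no one supposes will go unrecorded. The case report form is not among the documents.

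Much of this stands. A reader might infer that mild events will not be recorded, or that the plan forbids it; the documents do not support either. They leave the matter open. But 8.31 uses the word for documenting as well as for reporting, and no other passage supplies the missing recording rule, so the reply shows how the text might be read rather than what it requires.

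Three further limits also stand:

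- A reader might infer that nothing at all is observed for safety after day 7. That is too strong, because vital signs continue to day 70.
- A reader might infer that the trial will reach a false conclusion of tolerability. Safety is neither an objective (section 2.0) nor an outcome measure (section 10.0), and section 13 plans no safety comparison, so no such conclusion is announced.
- It is tempting to size the defect by the upper confidence bound when no events are seen in 6 or 12 subjects. That bound depends on the sample size alone and would be the same after the fix. An assumed fraction of events lost would have no support in the documents either.

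**Conclusion.** The point holds as a gap in the recording rule. As written, mild symptoms found at the Appendix I visits need not be documented, and the judgement that decides it is undefined and can differ between the groups. This is more than a missing definition: one filter governs both documenting and reporting, and separating them changes what is captured.

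The exposed part of follow-up is 63 of 70 days and three scheduled assessments per subject. That describes where the gap matters most; it is not an estimate of events lost, which the documents do not allow. The conclusion assumes that no unseen case report form or site manual already requires every event to be recorded. If one does, what remains is to bring 8.31 and 12.0 into line with it. The change is a cheap improvement that should be made before enrolment, because mild symptoms not noted at a visit cannot be reliably recovered later.

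**What to change.** 1. **Section 8.31.** Separate the two rules, for example: *Every adverse event found at the Appendix I visits is recorded on the case report form with onset date, severity on a stated scale, and relatedness. Events meeting the definition of significant given here are also reported to the IRB within the stated time.* Supply the definition and complete the template sentence on event types and timing.
2. **Symptom checklist.** Ask the 8.11 symptoms as a fixed list before dosing on day 0 and at each later visit, with the same wording in both groups. The pre-dose answers separate new symptoms from background complaints, which matters most in the CF group.
3. **Section 12.0.** Name adverse events among the data collected.
4. **Section 13.** Add a listing or simple table of adverse events by group with dose shown. A full cross-tabulation would be too thin: 2 groups × 3 dose tiers = 6 cells, or 12 / 6 = 2 subjects per cell on average.

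The cost is a few sentences, a one-page form, a little more recording time at visits that already take place, and more minor background events in the listings. No visit, blood draw, dose or clinical rule changes.
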